# 5. Statistical principles and analysis

## 5.1. Confidence intervals and p-values

The two-sided significance level for statistical tests will be 5 %. Differences in means and proportions will be presented with a 95% confidence interval (CI) and a p-value. All primary, secondary and exploratory measures will be presented.

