#### 5.4.2 Self-reported outcomes

Primary, secondary and exploratory outcomes are calculated and presented in means of scores at 8 months follow-up. In the protocol we wrote:

“The main outcome measure is activity engagement, measured by POES-S. To test the research hypothesis, the differences between the intervention group and the control group will be analyzed using ANOVA to determine the statistical significance. Effect sizes to judge clinical relevance will be calculated by Cohen’s d. In accordance with the intention-to-treat principles,

“multiple multivariate imputations” will be used and all co-variates of supposed prognostic significance will be used to impute a distribution of missing data.

The continuous power measurements will be analyzed with a repeated measurement model in mixed model analyses with unstructured variance. The prerequisite for using this analysis and for the use of multiple imputations is that data are missing at random or data missing completely at random as opposed to non-ignorable nonresponse. This distinction is important as repeated measurements and multiple imputations are both models based on a statistical estimation of non-existent responses, and the prerequisites for this estimation must be met for the analyses to be valid.” ([name] et al, 2020)

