### 5.5 Sensitivity analyses

No adjustments will be made in the primary analyses other than for stratification variables.

Sensitivity analyses are made with:

- Adjustment for baseline differences for those baseline characteristics with unequal/skewed baseline means and that can thus be associated with the outcome. Baseline characteristics in this case include (in addition to stratification variables) diagnosis, age, site and functioning) and self-reported outcome measures at baseline. Baseline tests will not be used exclusively in judging whether to include in the sensitivity analysis. Inclusion will be based on whether the groups are different to the extent that it could affect the analyses. The selection will be guided by CH.
- Imputations of missing values representing “worst” and “best” case of imputations. We will make two analyses: one where we in both groups replace imputations with “worst” case defined as the 90 percentiles from the imputed value and one where we in both groups replace imputations with “best” case defined as the 90 percentiles from the imputed value.
- The observed data.

Sensitivity analyses will be made for the primary outcome.

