## 5.9 Missing data

Multiple imputations will be used to address the issue of missing data. If possible, multiple multivariate normal regression imputations (Markov Chain Monte Carlo (MCMC)) will be used. This is possible if all imputed data follow the same distribution (e.g. are scale variables). A table of auxiliary variables are made based on the list of variables used in the MA&R project. These are chosen for being theoretically associated with the specific outcome. Also, variables that are predictive for missing data are included. This selection will be based on whether there is skewed dropout for the specific outcome variable. In the cases of extreme distributions predictive mean matching will be used instead of multivariate normal imputations. All variables in the model will also be included in the imputation model. We will perform at least 100 imputations for each analysis.

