**Table 1. Overview of outcomes**

Outcome measure no	Outcome	Source	Outcome measure	Definition of outcome and calculation	Variable properties	Higher/lower score indicates better outcome	Collected at 8-months follow-up
#1	Primary	Self-reported	Activity engagement (POES-S)	Calculated and presented as mean sum of points/scores	Numerical variable. 9 items. Items rated: 1-4. Scale from 9-36	Higher	x
#2	Secondary	Self-reported	Functioning (WHODAS – 12 items)	Simple scoring or Complex scoring (ITEM RESPONSE THEORY) Computer program available from WHO website  Calculated and presented as mean sum of points/scores	Numerical variable. 12 items. Items rated: 1-5. Scale from 12-60  Metric range from 0-100	Lower	x
#3	Secondary	Self-reported	Recovery (Questionnaire about the processes about recovery (QPR) 15 item)	Calculated and presented as mean sum of points/scores	Numerical variable. 15 items. Items rated: 0-4. Scale from 0-60	Higher	x
#4	Secondary	Self-reported	Quality of life (Manchester short assessment of quality of life (MANSA))	Calculated and presented as mean sum of points/scores.	Numerical variable. 12 items. Items rated: 1-7. Scale from 12-84	Higher	x
#5	Secondary	Self-reported	Health-related quality of life (EQ-5D-3L)	Calculated and presented as a weighted mean on a scale	Numerical variable. 5 items. Each combination of answers on items is provided with a weight/number between 0-1.	Higher	x
#6	Explorative	Self-reported	Functioning (WHODAS 2.0 36 items)	Simple scoring or Complex scoring	Each item rated 1-5 Total scale score: 36-180	Lower	x

		(domain score and total score))	Calculated and presented as a mean sum of points/scores	Domain scale score: Each domain contains between 5 to 8 items. (complex scoring) metric range 0-100		
--	--	---------------------------------	---	---	--	--

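### SAP section 5.5 defines the worst and the best case for missing POES-S scores by the same 90th percentile, so a high-score case is run twice and a low-score case never

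*SAP*

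**What the plan says.** Section 5.5 lists three sensitivity analyses: adjustment for baseline differences, a worst/best pair of replacements for imputed values, and the observed data. The worst run replaces imputed values, in both groups, with a "case defined as the 90 percentiles from the imputed value and one where we in both groups replace imputations with" the other case, which is the "best” case defined as the 90 percentiles from the imputed value". The scope is the primary outcome only: "Sensitivity analyses will be made for the primary outcome".

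That outcome is POES-S at eight months. Appendix 1, Table 1 gives its scale ("Numerical variable. 9 items. Items rated: 1-4. Scale from 9-36") and marks a higher score as the better one.

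Three other places bear on the point:
- Section 5.4.2 makes the validity of the imputation and mixed-model analyses depend on "data are missing at random or data missing completely at random as opposed to non-ignorable nonresponse".
- Section 5.9 sets the imputation effort ("We will perform at least 100 imputations for each analysis") but does not mention the two cases.
- Section 5.1 requires that "Differences in means and proportions will be presented with a 95% confidence interval (CI) and a p-value".

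**The concern.** Two analyses with opposite labels have the same percentile, the same groups and the same outcome. Read literally, they are one analysis. Because higher POES-S is better, the 90th percentile is the favourable end, so the case that disappears is the unfavourable one.

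This matters because the pair is the only planned look at non-ignorable missingness. Covariate adjustment and the observed-data analysis do not examine it.

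If the duplication goes unnoticed, a favourable-score result is reported under the label worst. If more scores are missing in MA&R, that result raises the apparent effect. If more are missing in control, both runs lower it and the upper bound is lost. If the duplication is noticed when the code is run, the rule has to be chosen with follow-up data in hand.

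**Working it through.** **Inputs from the SAP.** Difference 3, SD 6, two-sided alpha 0.05, power 0.80, 64 per arm (section 3.3; two-sidedness from section 5.1); at least 100 imputations (section 5.9); higher POES-S is better (Table 1).

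**Inputs assumed.** Missing rates by arm, and a correlation r = 0.5 between baseline and eight-month scores (range 0.3 to 0.7). The SAP gives neither.

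**The plan's own figure.** The normal formula gives 2 × (1.96 + 0.8416)² × 6² / 3² = 62.8, so 63 per arm. The t-test version gives 63.77, so 64 per arm and 128 in total, as stated. The sample size is not in question.

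**Closed form.** The 90th percentile of a normal distribution lies 1.2816 SD above its centre, and the 10th the same distance below. A participant's imputed values given baseline have SD 6 × √(1 − r²), which is 5.20 at r = 0.5. The shift per missing participant is therefore 1.2816 × 5.20 = 6.66 points. The difference between arms changes by

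6.66 × (share missing in MA&R − share missing in control),

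added for the 90th percentile and subtracted for the 10th.

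| Missing MA&R / control | 10th percentile (corrected worst) | 90th percentile (best) | Both runs as written |
|---|---|---|---|
| 25% / 15% | 3 − 0.67 = 2.33 | 3 + 0.67 = 3.67 | 3.67 |
| 30% / 10% | 3 − 1.33 = 1.67 | 3 + 1.33 = 4.33 | 4.33 |
| 15% / 25% | 3 + 0.67 = 3.67 | 3 − 0.67 = 2.33 | 2.33 |
| 20% / 20% | 3.00 | 3.00 | 3.00 |

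At 25%/15%, r from 0.3 to 0.7 gives 2.27 to 2.45 for the 10th percentile and 3.73 to 3.55 for the 90th. If the percentile is taken from a distribution with the full SD of 6, the shift is 1.2816 × 6 = 7.69. At 30%/20% the pair is then 2.23 and 3.77, against 3.77 twice as written. The conclusion does not depend on that reading.

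**Simulation.** 2,000 trials per scenario, 64 per arm, 100 regression imputations, values missing completely at random within arm, r = 0.5, scores unbounded because the SAP gives no mean.

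| Missing counts MA&R / control | Multiple imputation under missing at random | 90th percentile | 10th percentile |
|---|---|---|---|
| 16 / 10 | 3.04 | 3.67 | 2.41 |
| 19 / 6 | 3.08 | 4.43 | 1.72 |
| 10 / 16 | 2.98 | 2.35 | 3.60 |
| 13 / 13 | 2.97 | 2.97 | 2.97 |

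These agree with the closed form. At 16/10, for example, 6.66 × 6/64 = 0.62, and 3.04 ± 0.62 gives 3.66 and 2.42.

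At 16/10 with direct replacement, the run labelled worst favours MA&R with p < 0.05 in 91% of trials as written, against 61% with the 10th percentile. Repeat simulations of 1,000 to 1,500 trials gave 88% to 90% and 56% to 60%.

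**Standard error.** Replacing each missing value by one number gives an SE of 1.08, close to the complete-data value 6 × √(2/64) = 1.06, so the uncertainty of imputation is lost. Multiple imputation under missing at random gives 1.16. Shifting every imputed value to centre on the percentile and then pooling gives the same point estimates (3.67 and 2.41) with SE 1.26, and p < 0.05 in 85% and 49%.

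With no true difference and 13/13 missing, rejection is 6.6% to 7.4% for single replacement, 5.1% to 5.3% for multiple imputation under missing at random, and 3% to 4% for shift and pool.

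**The case against.** The best case against giving this much weight is as follows.

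- It reads as a slip. The labels, the stated 90 for best and the direction of the scale together point to the 10th percentile, and two identical outputs would probably be noticed. Section 5.2 also commits the team to report major deviations from the SAP. This makes harm less likely, but a plan should not need the reader to infer the rule.
- The effect comes only from unequal dropout. At 14/12 missing it is about 6.66 × 2/64 = 0.2 points either way, and at equal dropout it is nil. This stands: the larger figures are illustrations and say nothing about this trial's actual dropout. Section 5.9 does, however, allow for dropout to be skewed.
- A correction now is also late. Enrolment ended in August 2020, follow-up is at about eight months, and the SAP is dated July 2021, so most follow-up data were probably already collected. This stands too, and is a reason to date and document the correction.
- The strict defect is the percentile alone. Pooling is a separate matter, and shift and pool has its own faults: it is mildly conservative, and it can push scores outside 9 to 36. Both are true. But section 5.5 does not say how a replaced percentile yields the interval and p-value that section 5.1 requires, so one sentence on procedure is needed in any case.

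**Conclusion.** The concern holds. Section 5.5 specifies one high-score run under two labels, and nothing elsewhere in the SAP supplies the low-score run. Under the assumptions above, the missing run would lie about 1.3 points from the one reported at 25%/15% missing (3.67 − 2.33) and about 2.7 points at 30%/10% (4.33 − 1.67), against a target difference of 3. With equal missingness in the two arms it would lie 0 points away.

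The primary analysis is not affected. This should be corrected before the sensitivity analyses are run, because it disables half of the only check on the missing-data assumption.

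**What to change.** For POES-S, define worst as the 10th percentile and best as the 90th percentile of each participant's imputed values, applied in both groups.

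Use one procedure for both runs. Add to each of a participant's 100 or more imputed values the distance from their mean to the chosen percentile, analyse every completed data set, and pool as usual. For a difference in means this gives the same estimate as direct replacement and keeps the between-imputation variance. State how shifted scores outside 9 to 36 are handled. Date the change, record whether outcome data by arm had been seen, and report it as a change to the SAP.

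Optionally, because runs in the same direction say little when dropout is similar in the two arms, add one pair with the arms moved in opposite directions, or a graded delta (tipping-point) analysis, labelled as a severe stress test.

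The cost is a few lines of SAP text and code. The corrected worst case will be significant less often if more is missing in MA&R, pooling widens the interval (SE about 1.26 against 1.08) and is slightly conservative, and the optional runs give a wider and less favourable range.

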## 5.6 Subgroup analyses

No subgroup analyses will be planned, as the sample size does not allow this.

## 5.9 Missing data

Multiple imputations will be used to address the issue of missing data. If possible, multiple multivariate normal regression imputations (Markov Chain Monte Carlo (MCMC)) will be used. This is possible if all imputed data follow the same distribution (e.g. are scale variables). A table of auxiliary variables are made based on the list of variables used in the MA&R project. These are chosen for being theoretically associated with the specific outcome. Also, variables that are predictive for missing data are included. This selection will be based on whether there is skewed dropout for the specific outcome variable. In the cases of extreme distributions predictive mean matching will be used instead of multivariate normal imputations. All variables in the model will also be included in the imputation model. We will perform at least 100 imputations for each analysis.

## 5.10 Additional statistical analyses

Additional to the planned analyses in the protocol we will:

- Calculate the effect size (based on Cohen's d) of the primary outcome POES- S at 8 months follow up.

## 5.11 Safety data

The following variables will be summarized for each randomization group at 8 months follow-up.

- Number of bed days and admissions (somatic indication)
- Number of bed days and admissions (psychiatric indication)
- Number of somatic outpatient visits
- Number of deaths from suicide and other causes
- Scores of The Clinical Global Impression – Severity of Illness Scale (CGI-S)

## 5.12 Statistical packages to be used to carry out analyses

We will primarily use the statistics program SPSS. Other statistical packages might be used for some analyses.

## 6. Appendix 1

**Table 1. Overview of outcomes**

Outcome measure no	Outcome	Source	Outcome measure	Definition of outcome and calculation	Variable properties	Higher/lower score indicates better outcome	Collected at 8-months follow-up
#1	Primary	Self-reported	Activity engagement (POES-S)	Calculated and presented as mean sum of points/scores	Numerical variable. 9 items. Items rated: 1-4. Scale from 9-36	Higher	x
#2	Secondary	Self-reported	Functioning (WHODAS – 12 items)	Simple scoring or Complex scoring (ITEM RESPONSE THEORY) Computer program available from WHO website  Calculated and presented as mean sum of points/scores	Numerical variable. 12 items. Items rated: 1-5. Scale from 12-60  Metric range from 0-100	Lower	x
#3	Secondary	Self-reported	Recovery (Questionnaire about the processes about recovery (QPR) 15 item)	Calculated and presented as mean sum of points/scores	Numerical variable. 15 items. Items rated: 0-4. Scale from 0-60	Higher	x
#4	Secondary	Self-reported	Quality of life (Manchester short assessment of quality of life (MANSA))	Calculated and presented as mean sum of points/scores.	Numerical variable. 12 items. Items rated: 1-7. Scale from 12-84	Higher	x
#5	Secondary	Self-reported	Health-related quality of life (EQ-5D-3L)	Calculated and presented as a weighted mean on a scale	Numerical variable. 5 items. Each combination of answers on items is provided with a weight/number between 0-1.	Higher	x
#6	Explorative	Self-reported	Functioning (WHODAS 2.0 36 items)	Simple scoring or Complex scoring	Each item rated 1-5 Total scale score: 36-180	Lower	x

		(domain score and total score))	Calculated and presented as a mean sum of points/scores	Domain scale score: Each domain contains between 5 to 8 items. (complex scoring) metric range 0-100		
--	--	---------------------------------	---	---	--	--

**Table 2. Safety measures**

Safety measure no.	Outcome measure	Source	Definition of outcome and calculations	Variable properties
1	Number of outpatient somatic visits from baseline to follow-up	Register	Number of visits are calculated as an incidence rate ratio based on the follow-up period. Total number is also presented.	Numerical variable. Minimum: 0 visits, no defined upper limit
2	Number of inpatient somatic bed days and admissions from baseline to follow-up	Register	Number of bed days and admissions are calculated as incidence rates and an incidence rate ratio based on the follow-up period. Total number is also presented.	Numerical variables. Minimum: 0 bed days, no defined upper limit
3	Number of inpatient psychiatric bed days and admissions from baseline to follow-up	Register	Number of bed days and admissions are calculated as an incidence rate ratio based on the follow-up period. Total number is also presented.	Numerical variables. Minimum: 0 bed days, no defined upper limit
4	Deaths from suicide and other causes from baseline to follow-up	Register	Total number of deaths is reported + stratified by cause of death: suicide and other	Numerical variable. Minimum: 0 deaths, upper limit is the total number of included participants
5	Symptoms severity (Clinical Global Impression – self report)	Self-reported	Calculated and presented as mean sum of points/scores	Numerical variable. 1 item, item rated 1-7 (Scale from 1-7)

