### 3. Study Methods

#### 3.1 Trial design

A multicenter two arm, parallel randomized controlled trial. Eligible participants were individuals with psychiatric disabilities, who were treated in one of three community mental health centers in Mental Health Center Copenhagen, or were citizens in the municipalities of Copenhagen, Svendborg or Odense. Included participants were allocated with a 1:1 ratio to either Meaningful Activities and Recovery (MA&R) a novel rehabilitation intervention, in addition to usual care, or usual care alone. The enrollment started at September 2018 and lasted to August 2020. MA&R lasts for about eight months and consists of 11 group sessions and 11 one-to-one sessions.

From the protocol ([name] et al, 2020)

“MA&R is delivered by a peer worker and an Occupational therapist. In addition to the planned sessions, the participants are offered individualized support to engage in meaningful activities. The MA&R is a manualized intervention, with a workbook developed for the participants to support learning and personal exploration. MA&R utilized various methods such as didactic presentations, peer exchange, direct experiences with activities and personal exploration. The MA&R contains two courses: MA&R I and MA&R II which complement each other. In MA&R I, the participants can explore and identify meaningful activities, while MA&R II supports anchoring new activities and habits in everyday life.”

Data was collected twice, baseline before randomization and at follow up, at the end of the intervention.

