### 3.3 Sample size calculation

Below numbers are retrieved from the protocol paper ([name] et.al 2020).

- Type 1 error set at: 0.05 ( $\alpha$ )
- Power: 0.80 ( $\beta$ )
- Difference in mean: 3 points
- within group standard deviation (SD): 6

From the protocol paper ([name] *et al.*, 2020): “The sample size is calculated based on the primary hypothesis to detect a minimal but clinically significant difference between the intervention group and the control group on POES-S (increased engagement in meaningful activities). In a recent RCT testing, the intervention Balancing Everyday Life (BEL) in a similar population as that in this study, Eklund et al. found a small effect of 1.4 points measured on POES-S ( $d = 0.27$ ) [21]. As MA&R has a more comprehensive format (in terms of duration and costs) than BEL, the clinically significant difference between the study groups is set to 3 points, corresponding to a moderate effect size (Cohens  $d = 0.5$ ). Based on the BEL trial, we assume the standard deviation in the study population to be 6. To achieve a statistical power of 80% and a significance level of 5%, a total of 128 participants must be included in this study; 64 in each group to detect this difference.”

No interim analyses were planned.

There were no guidelines for stopping the trials early.

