## 4.4 Baseline characteristics

Sex, age, housing/marital status, educational level, diagnosis, work status, functional level (assessed by researcher). Register-based and self-reported baseline outcome measures will also be summarized.

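### Cheap improvement: the visit and admission rate ratios in SAP Table 2 could also be reported adjusted for each participant's own service use before baseline

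*SAP*

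**What the plan says.** - **Table 2, rows 1 to 3.** Somatic outpatient visits, somatic bed days and admissions, and psychiatric bed days and admissions come from registers and run from baseline to follow-up. For row 1, "Number of visits are calculated as an incidence rate ratio based on the follow-up period". Rows 2 and 3 are worded in the same way. Totals are also shown. No count model, covariate or pre-baseline period is named.
- **Section 5.11.** The safety variables are summarized by randomization group.
- **Section 4.4.** "Register-based and self-reported baseline outcome measures will also be summarized". No look-back window is given.
- **Section 3.2.** Randomization is stratified by sex only.
- **Section 5.5.** Adjustment for baseline differences is a sensitivity analysis, and its scope is limited: "Sensitivity analyses will be made for the primary outcome".
- **Section 5.1.** Confidence intervals are promised for differences in means and proportions. Rate ratios are not mentioned.

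**The concern.** Use of hospital services is plausibly concentrated in a minority of people who are heavy users both before and after enrolment. Nothing in the design balances such people between arms. If one arm starts with more of them, a ratio built from follow-up counts alone will tend to lean the same way. A reader who sees more prior admissions in one arm's baseline table, and then a crude ratio above 1, cannot tell how much of the second reflects the first. An imbalance in the other direction could mask a real increase.

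The SAP accepts this reasoning for POES-S, where Section 5.5 provides a baseline-adjusted analysis. It does not extend it to the safety counts, although Section 4.4 suggests the covariate will be at hand.

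**Working it through.** **1. The plan's own figure.** Section 3.3 gives "Difference in mean: 3 points" and "within group standard deviation (SD): 6", with power 0.80; Section 5.1 gives two-sided 5%; Section 3.1 gives 1:1 allocation.
- Normal approximation: n per arm = 2(1.96 + 0.842)² × 6²/3² = 2 × 7.849 × 4 = 62.8, so 63 (126 in total).
- Two-sample t-test: power 0.7952 at 63 and 0.8015 at 64 per arm, so 64 per arm.

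The stated total of 128 is reproduced. The SAP gives no figure for the safety ratios, so every rate below is an assumption.

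**2. What register baseline can mean.** Every outcome in Table 1 is self-reported. The only register-sourced measures are Table 2, rows 1 to 4: visits, bed days, admissions and deaths. Deaths have no baseline value. The phrase in Section 4.4 therefore most sensibly refers to prior visits, bed days and admissions.

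**3. Chance spread of the crude ratio.** With mean m events per person, between-person dispersion k, equal follow-up and 64 per arm:

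SD(log ratio) ≈ √[2(1/m + k)/64]

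- Visits, m = 3, gamma shape 0.7 (k = 1/0.7 = 1.429): √[2 × 1.762/64] = 0.235. Simulated: 0.242 to 0.253.
- Admissions, m = 0.6, shape 0.5 (k = 2): √[2 × 3.667/64] = 0.339. Simulated: 0.335.

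Formula and simulation agree. At SD 0.339 the 95% chance range under no effect is exp(±1.96 × 0.339), about 0.51 to 1.94.

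**4. Gain from adjustment, gamma-distributed rates** (400 trials per setting, no true effect, negative binomial fits with and without log(1 + baseline count)). Variance reduction = 1 − (adjusted SD/crude SD)².
- Visits, fully persistent: 1 − (0.148/0.253)² = 0.66.
- Visits, 60% of people persistent: 1 − (0.223/0.242)² = 0.15.
- Admissions: 1 − (0.291/0.335)² = 0.25.

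Repeat simulations with the same means and shapes gave:
- Visits: 53 to 68% at full persistence, 7% or less at 60%, none at 30%.
- Admissions: 22% at full persistence, 8% at 60%, none at 30%.
- Rarer admissions (mean 0.2, shape 0.3): 5% at full persistence, none below it.

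**5. Gain from adjustment, log-normal rates** (800 trials per setting, look-back 1.5 times follow-up, covariate log(prior count + 0.5)). Stability is the share of log-rate variance that persists over time.

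| Mean | k | Stability | SD crude | SD adjusted | Variance reduction | Correlation with prior-use imbalance, crude → adjusted |
|---|---|---|---|---|---|---|
| 0.5 | 1 | 0.3 | 0.311 | 0.313 | −1% | 0.10 → 0.01 |
| 0.5 | 3 | 0.5 | 0.390 | 0.372 | 9% | 0.22 → 0.02 |
| 0.5 | 3 | 0.8 | 0.412 | 0.358 | 25% | 0.43 → 0.07 |
| 2 | 1 | 0.8 | 0.212 | 0.176 | 31% | 0.46 → 0.03 |
| 2 | 3 | 0.5 | 0.324 | 0.286 | 22% | 0.27 → −0.03 |
| 2 | 3 | 0.8 | 0.324 | 0.230 | 50% | 0.51 → 0.09 |

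Over all twelve settings, a ratio beyond 1.5 or below 0.67 arose by chance in 4 to 31% of trials crude and in 2 to 28% adjusted.

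**The case against.** The strongest reply is that nothing here is wrong. An unadjusted rate ratio is a legitimate choice for a safety summary, it is unbiased under randomization, and wide swings are ordinary sampling error in a trial of 128. That stands, and it is why the point is only an improvement. A reader might infer that the crude ratios are biased or that the SAP contradicts itself; neither follows.

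A reader might also take these ratios to be the only comparative safety evidence. They are not: Section 5.11 and Table 2, rows 4 and 5, also report deaths and CGI-S by arm, and bed days have rate ratios too.

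Three further objections stand in part.
- **Availability.** Section 4.4 does not name prior visits or admissions. Reading it as prior service use is the sensible interpretation but still an inference. If those counts are not extracted, the fix needs an additional register extraction.
- **Size.** The large gains need frequent events and highly stable use. With partial persistence most chance signals remain after adjustment.
- **Scope.** The heavy-user argument applies to bed days as well. They are left out because days accrue within a stay, so how to model them is a separate question.

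What the objections do not remove is that adjustment brings the correlation between the safety ratio and observed imbalance in prior use close to zero in every setting examined.

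**Conclusion.** The point holds as a low-priority improvement. Table 2, rows 1 to 3, uses follow-up counts only, randomization balances sex only, and the baseline adjustment in Section 5.5 stops at the primary outcome. The crude visit and admission ratios therefore carry any chance imbalance in prior use into the safety comparison.

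The variance of the log rate ratio would fall by about 0 to 20% for admissions or partly persistent use, reaching about 25% for admissions when use is very stable. For frequent events it was 31 to 50% at stability 0.8. About 50 to 70% is an upper bound, for frequent and fully persistent visits. For rare events the gain is nil or close to it. These sizes rest on assumed rates, dispersion and persistence and on 64 per arm. A reader might expect adjustment to settle whether a raised ratio is a real signal; the chance figures above show that it does not.

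**What to change.** In Table 2, rows 1 to 3, keep the crude totals and crude rate ratios. Beside them, for visits and admissions, report an adjusted rate ratio with 95% CI from a negative binomial model with:
- log follow-up time as offset;
- arm and sex;
- log(1 + the participant's own count of the same event in a pre-baseline window).

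State in Section 4.4 which register measures are summarized at baseline and over what look-back window, and fix that window before arms are compared. State also that only the crude figures will be given where counts are too sparse for the model to be useful.

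Cost: a few sentences in the SAP and one covariate. No new data source is needed if the register baseline is extracted as Section 4.4 implies; otherwise an additional extraction is required. Section 5.12 already allows packages other than SPSS. The downsides are one more pre-specified choice (the window) and a model that may add nothing for very sparse counts.
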